### C.4.5 Enrollment and Randomization

Prior to randomization and enrollment of a subject, the following must occur:

- Confirm patient signed informed consent
- Confirm patient meets all of the inclusion and none of the exclusion criteria, including approval by the Heart Team

Subjects will be considered enrolled into the trial at the time of randomization (i.e. time of treatment assignment). Randomization will occur only if the patient meets all inclusion criteria and does not meet any exclusion criteria and has been assessed by the Heart Team as being an appropriate candidate for randomization in the SURTAVI trial.

Due to the inclusion/exclusion criteria, not all patients that consent to the trial will be enrolled. All sites will be required to maintain a record of patients screened for the trial meeting general inclusion criteria who have signed the approved informed consent document. For subjects that do not meet trial criteria, the reason for not continuing in the trial must be documented and recorded in the EDC system. Patients consented but not randomized will be considered screen failures and no further trial-related follow-up will be required.

Subjects must have their TAVI or SAVR procedure no later than 30 days post-randomization.

Trial randomization will not be blinded. Once randomization is complete and a treatment arm is assigned, crossover from SAVR to TAVI treatment is not permitted. The sponsor will strictly monitor device dispensation to ensure that only those subjects randomized to the TAVI treatment arm receive the Medtronic CoreValve™ or CoreValve™ Evolut™ R TAV.

Distribution of the subjects within the trial groups will be controlled at the implanting sites by means of central randomization using interactive voice/web randomization service (IXRS). The randomization scheme will be securely stored at the IXRS provider.

---

 Based on protocol design, the time of enrollment will be the same as randomization which is a deviation from ISO 14155 (2011).

Randomization with an assignment to the treatment arm or control arm (TAVI or SAVR) will be executed in a 1:1 ratio. Stratified randomization by investigational site and by the need for coronary revascularization will be used to ensure subjects will be allocated to each comparison group proportionately. Additionally, a blocked randomization scheme with random block sizes will be used within each stratum.

#### C.4.6 Baseline Assessments

The following baseline assessments should occur within 14 days prior to the index procedure.

- Physical examination
  - Vital signs
  - Major system findings
  - Skin assessment – refer to Radiation Exposure and Data Collection, **Appendix R.23**
- NYHA classification
- Concomitant medications
  - Use of relevant medications (diuretics, aspirin, anticoagulants, ACE-I, ARB, beta-blockers, statins and anti-platelets)
- Routine Laboratory Tests:
  - Complete Blood Count
    - White Blood Count
    - Hematocrit
    - Hemoglobin
    - Platelet Count
  - Creatinine and Creatinine Clearance
  - Cardiac Enzymes (CK/CK-MB)
  - International Normalized Ratio (INR), if applicable
  - Activated Partial Thromboplastin Time (aPTT)
  - B-type Natriuretic Peptide (BNP) or NT-proBNP
  - Liver Panel:
    - ALT
    - AST
    - Albumin
  - Sodium
  - Potassium
- Neurological Assessments:
  - National Institute of Health Stroke Scale (NIHSS)
  - Modified Rankin Score (mRS)
  - Mini-Mental State Exam (MMSE-2:SV)
  - Additional Neurological testing:
    - Visual Fields Testing
    - Gait Assessment
    - Hand Function
    - Writing Evaluation
    - Drawing Assessment
- 12-lead Electrocardiogram (ECG)
- 6 Minute Walk Test
- Quality of Life Questionnaires
  - Questionnaires may be administered any time after the subject has provided informed consent but should be collected prior to informing the subject of their treatment assignment
- Adverse Event Review

---

### C.4.7 *Transcatheter Aortic Valve Implant or Surgical Aortic Valve Replacement Procedure*

#### C.4.7.1 TAVI

##### **General Procedural Considerations**

Transcatheter Aortic Valve Implantation (TAVI) requires meticulous preparation and typically a multi-disciplinary team approach involving among others, interventional cardiologists, cardiac imaging specialists, cardio-thoracic surgeons and anesthesiologists.

***Within the United States, additional requirements apply for composition of the intra-operative team for TAVI procedures. Requirements are outlined in Appendix R.25.***

In case of significant coronary artery disease that requires revascularization, the Heart Team will assess the feasibility of performing PCI simultaneously with the TAVI procedure based on the coronary lesion characteristics. When it is anticipated PCI can be performed in timely fashion with only a limited amount of additional contrast medium it is encouraged to perform PCI concomitant with the TAVI. When PCI is deemed challenging requiring relatively more time and contrast medium, staged PCI is recommended: TAVI will then be performed at least 7 days after PCI.

The implantation procedure itself takes place either in a catheterization laboratory with adequate hygiene precautions or ideally in a hybrid operating room equipped for state-of-the-art transcatheter and/or surgical procedures.

The execution of the TAVI involves an operating team typically consisting of 1 or 2 operators, an anesthesia team and at least 2 nurses/technicians. Medtronic representative(s) (eg. Therapy Development Specialists, proctors, etc.) may be present during TAVI procedures for training process, to perform valve loading or to provide general case support.

Both the dedicated “valve team” and the operators should have the expertise to select the appropriate access route and device size on a patient-per-patient basis.

All patients undergoing TAVI should be treated using the iliofemoral access route by default (first treatment strategy). Additional non-iliofemoral access routes will only be used in case iliofemoral access is not feasible. Alternative access is limited to subclavian and direct aortic.

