### **C.4.7.2 Surgical Aortic Valve Replacement**

#### **Minimum Standards for Surgical Aortic Valve Replacement**

Subjects randomized to SAVR should be treated according to the surgeon and hospital's standard practices. The surgeon or co-surgeon performing the SAVR must be a trial investigator for the site. The choice of surgical valve is left to the discretion of the investigator. **However, the use of a bioprosthetic valve is required.**

**SAVR must be conducted as an isolated procedure with exception of subjects that have been randomized to SAVR with revascularization (eg. Aortic replacement or Maze procedures are not permitted).** In cases of significant coronary artery disease that requires revascularization coronary artery bypass grafting (CABG) will be conducted concomitantly with SAVR.

Additional concomitant cardiac and non-cardiac procedures are not permitted with the exception of the procedures outlined under Additional Procedural Considerations.

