##### Day 0 = day of index procedure (TAVI or SAVR):

- 30 days (- 7 days and + 14 days)
- 3 months (90 ± 14 days)
- 6 months (180 ± 30 days)
- 12 months (365 ± 30 days)
- 18 months (545 ± 60 days)
- 24 months (730 ± 60 days)
- 3 years (1080 ± 60 days)
- 4 years (1440 ± 60 days)
- 5 years (1800 ± 60 days)

All randomized subjects will complete long-term follow-up through at least 5 years. Based on clinical assessments or regulatory requirements, follow-up may be extended to up to 10 years post-index procedure. Upon completion of the final protocol visit (discontinuation) subject participation will be considered complete and the patient should then be followed per the local standard of care for their condition.

Note: For subjects where the Index Procedure is never attempted (eg. subject withdraws consent for the procedure but agrees to complete follow-up) follow-up intervals will be calculated from the 31st days post-randomization (i.e. the 1st day after the 30 day window from randomization to complete the Index Procedure).

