### *C.5.2 Reporting*

Investigators are required to keep records on “all relevant observations, including records concerning adverse device effects (whether anticipated or unanticipated)” [21 CFR 812.140; ISO 14155 (2011)]. Adverse event collection will begin from the point of trial enrollment to trial closure. All new or worsening (from baseline) adverse events and technical observations will be captured on the AE eCRF through the 24-month follow-up visit. It is the responsibility of the Investigator to assess the subject for adverse events and capture the required adverse event information on the AE eCRF.

Once a subject has completed their 24-month scheduled follow-up visit only serious adverse events, major adverse events, cardiovascular events, device-related adverse events, including device related technical observations, unanticipated adverse device effects (UADE) or unanticipated serious adverse device effects (USADE), all strokes (CVAs) and deaths will be required to be reported. Reference section C.5.1 Adverse Events for event definitions and criteria. Medtronic representatives or their designees will conduct monitoring visits to review source documentation and verify the complete and accurate capturing of adverse events.

The Investigator must also notify the responsible IRB/MEC regarding new and significant safety information and any event identified by Medtronic that requires expedited FDA, and/or local regulatory agency, reporting as serious, unexpected, and related to the investigational device. It is the responsibility of the investigator to ensure site specific IRB/MEC safety reporting requirements are met.

Medtronic Clinical will ensure all device-related adverse events and all procedure-related SAEs are processed according to internal policies and procedures. When necessary, Medtronic Field Assurance will respond to sites in writing with the findings related to the product experiences.

The general procedure for investigators reporting any adverse event is as follows:

- Report the event to Medtronic as soon as possible but no later than the timeframes outlined below. (At the time of Site Initiation, sites will be provided with the telephone and other applicable contact information of the appropriate Medtronic designee).
- Complete all sections of the Adverse Event eCRF.
- Each unique event/diagnosis must be documented separately.

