## C.6 Statistical Methods and Analysis

### C.6.1 Statistical Considerations and Analysis

This section describes the statistical considerations and analysis plans for the SURTAVI trial. The statistical analysis will be performed by the statistics department of Medtronic. As primary analysis all randomized subjects will be analyzed following the modified intention to treat (mITT) approach; ie. analyses will be conducted on the cohort of subjects who undergo an attempted trial treatment, analyzed according to the randomized assignment. A secondary analysis of key objectives will be performed according to the therapy actually received.

Roll-in subjects will not be included in the primary or secondary analysis; however, the data will be summarized separately with descriptive statistics.

All follow-up periods are defined as the number of days after the procedure date.

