- The incidence of conduction disturbance requiring permanent pacemaker implantation will be provided at 30 days, 6 months, 12 months, 18 months, 24 months, and annually thereafter up to 5 years, separately for new onset and pre-existing conduction disturbance. The statistical method will be the Bayesian version of a comparison of proportions (with predictions).
8. Change in NYHA class from baseline at 30 days, 6 months, 12 months, 18 months, 24 months, and annually thereafter up to 5 years.
- For each subject with paired data, the number of classes changed from baseline (-3, -2, -1, 0, 1, 2, or 3) will be calculated at 30 days, 6 months, 12 months, 18 months, 24 months, and annually thereafter up to 5 years. The endpoint will be evaluated between groups using a Bayesian version of a t-test.
9. Change in distance walked during 6-minute walk test (6MWT) from baseline to 30 days, baseline to 12 months, and baseline to 24 months.

All subjects who are able to perform the six-minute walk evaluation at the time of the follow-up visit will be included in the analysis.

The endpoint will be evaluated using a Bayesian version of a t-test.

10. Ratio of days alive out of hospital versus total days alive assessed at 12 months and 24 months follow-up.

The proportion of post procedure days alive out of hospital against total days alive will be compared between groups at 12 and 24 months. The numerator will be the number of days alive out of hospital, and the denominator will be the number of post procedure days alive as of the last follow-up date. All hospitalizations will be included in this analysis, including hospitalization for device implant.

In addition, days alive out of hospital will be compared between groups at 12 months and 24 months.

The endpoint will be evaluated using a Bayesian version of a t-test.

11. Quality of Life (QoL) change from baseline at 30 days, 3 months, 6 months, 12 months, 18 months, 24 months, and annually thereafter up to 5 years.

The Kansas City Cardiomyopathy Questionnaire (KCCQ), SF-36, and EuroQoL (EQ-5D) will be assessed at baseline, 30 days, 6 months, 12 months, 18 months, 24 months, and annually thereafter up to 5 years. SF-36 and EQ-5D will also be assessed at 3 months. All subjects completing the questionnaires will be evaluated and the reasons for missing data will be provided.

The endpoint will be evaluated using a Bayesian version of a t-test .

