where  $\mu_{TAVI}$  and  $\mu_{SAVR}$  denote the mean improvements in the KCCQ score from baseline to 30 days. For subjects with KCCQ score at both baseline and 30 days, the improvement in KCCQ will be calculated as  $KCCQ_{30day} - KCCQ_{baseline}$ . This objective will be evaluated using a Bayesian version of a two-sample t-test (see Section C.11). The posterior probability  $P(H | data)$  will be calculated and compared to a threshold of 0.95.

5. Length of index procedure hospital stay after TAVI vs. SAVR (secondary objective #18). The hypothesis of interest is

$$H: \mu_{TAVI} < \mu_{SAVR}$$

where  $\mu_{TAVI}$  and  $\mu_{SAVR}$  denote the mean length of index hospital stay. This objective will be evaluated using a Bayesian version of a two-sample t-test (see Section C.11). The posterior probability  $P(H | data)$  will be calculated and compared to a threshold of 0.975.

6. Transvalvular mean gradient at 12 months (superiority): TAVI vs. SAVR (secondary objective #12). The hypothesis of interest is

$$H: \mu_{TAVI} < \mu_{SAVR}$$

where  $\mu_{TAVI}$  and  $\mu_{SAVR}$  denote the average mean gradient from at 12 months, measured in mmHg. This objective will be evaluated using a Bayesian version of a two-sample t-test (see Section C.11). The posterior probability  $P(H | data)$  will be calculated and compared to a threshold of 0.975.

7. Effective orifice area at 12 months (superiority): TAVI vs. SAVR (secondary objective #12). The hypothesis of interest is

$$H: \mu_{TAVI} > \mu_{SAVR}$$

where  $\mu_{TAVI}$  and  $\mu_{SAVR}$  denote the mean effective orifice area at 12 months, measured in  $cm^2$ . This objective will be evaluated using a Bayesian version of a two-sample t-test (see Section C.11). The posterior probability  $P(H | data)$  will be calculated and compared to a threshold of 0.975.

8. Change in Kansas City Cardiomyopathy Questionnaire (KCCQ) score from baseline to 30 days (superiority): TAVI vs. SAVR (secondary objective #11). The hypothesis of interest is

$$H: \mu_{TAVI} > \mu_{SAVR}$$

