#### C.6.13.2 Economic Outcomes/Cost-Effectiveness

Data on resource utilization will be collected for the index hospitalization and through long-term follow-up for all enrolled subjects. These resource items will include number and duration in-patient stays in hospital by type of unit (eg. intensive care, high-dependency care and standard ward care); number of clinic visits (by type of physician); and details of the main procedure undertaken. As part of the trial analysis, resource use estimates will be presented by randomized group (eg. mean per patient plus standard deviation). This data, together with the EQ-5D data will provide an important input into cost effectiveness analysis. However, as such analysis is likely to be based on a modeling framework, to include evidence from a number of sources (eg. a meta-analysis of other TAVI trials) and to vary according to the jurisdiction of interest, it is appropriate to detail the methods in separate protocols and analysis plans.

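### With Day 0 set at TAVI, nights and events of a separately admitted staged PCI fall outside labeling claims #5 and #13 to #16, while CABG done with SAVR is counted in full

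*Combined protocol and SAP*

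**What the plan says.** Randomization is stratified by need for coronary revascularization (C.3.9, C.4.5, C.6.5.2), so that stratum compares TAVI plus PCI with SAVR plus CABG.

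- **PCI in the TAVI arm.** Concomitant PCI is encouraged and staging is left to the operator (C.3.9). When PCI would need more time and contrast, C.4.7.1 says "staged PCI is recommended: TAVI will then be performed at least 7 days after PCI".
- **CABG in the SAVR arm.** C.4.7.2 says "coronary artery bypass grafting (CABG) will be conducted concomitantly with SAVR".
- **Clock.** C.4.9 sets "Day 0 = day of index procedure (TAVI or SAVR", and C.6.1 repeats the rule for the analysis: "All follow-up periods are defined as the number of days after the procedure date".
- **Claim #5.** C.6.10.1 tests "Length of index procedure hospital stay after TAVI vs. SAVR (secondary objective #18"; C.6.8.1 item 18 describes this as the stay for TAVI or SAVR.
- **Claims #13 to #16.** MACCE, major vascular complications, major or life-threatening bleeding, and all strokes are each counted to 30 days, or to discharge if that is later.
- **Claims #9 and #10.** C.6.8.1 item 10 says "The proportion of post procedure days alive out of hospital against total days alive will be compared between groups at 12 and 24 months". The same item also says that every hospitalization is included.
- **Adverse events.** C.5.2 says "Adverse event collection will begin from the point of trial enrollment to trial closure", and enrollment is the moment of randomization (C.4.5).

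**The concern.** A PCI staged after randomization is part of the randomized strategy, just as CABG is. CABG nights and complications fall on or after Day 0 and are counted. The nights and complications of a separately admitted PCI fall before Day 0, and no rule in the sections cited here brings them back in. For these subjects, following the stated time origin gives a one-sided result.

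The staged cases are not a random subset: by C.4.7.1 they are the more demanding interventions. The trial is unblinded and staging is at the operator's discretion. An open-label decision, available in one arm only, thus determines whether revascularization morbidity is counted.

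At stake are superiority claims intended for labeling. Claim #5 is the first test in superiority subfamily #2 (C.6.10), and the later claims are reached only if it succeeds.

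**Working it through.** **Plan's own figures.** The plan states no figure on this point. Its sample size supplies the arm size: the single-look 1258 reproduces by Farrington-Manning (628.6, rounded up to 629 per arm), and the planned 1600 mITT subjects at 1:1 give 800 per arm.

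**Step 1: where a staged PCI falls.** Exclusion 7 bars PCI in the 30 days before randomization. C.4.5 requires TAVI no later than day 30 after randomization. C.4.7.1 sets a gap of at least 7 days. PCI done for the assigned strategy therefore falls on about days 0 to 23 (30 − 7 = 23) and TAVI on days 7 to 30, so PCI always precedes Day 0.

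**Step 2: what each endpoint counts.**

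| Endpoint | Separate PCI admission before TAVI | CABG with SAVR |
|---|---|---|
| #5 length of stay | nights outside the TAVI stay | nights inside |
| #13 to #16 | events between PCI and TAVI precede the window | inside |
| #9, #10 | unclear: post-procedure clock, but all hospitalizations included | inside |

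For MACCE, the MI definition in O.2 is also tied to time after the index procedure, so an MI between PCI and TAVI fits neither of its two categories.

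**Step 3: size.** The documents give no staging share (f), nights per staged PCI (d), complication rate (q), SD or control rate. All are assumptions: f 2 to 20%, d 1 to 4, q 2 to 10%, SD of stay 4 to 10 days, control rate 5 to 15%.

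- Amount omitted from the TAVI mean or rate: b = f × d, or b = f × q (the latter assumes no second event in the same subject).
- One-sided error if the arms were truly equal with everything counted: 1 − Φ(1.96 − b/SE), against a nominal 0.025.
- SE for stay: SD × √(2/800) = 0.05 × SD, which is 0.20 day at SD 4 and 0.50 day at SD 10.

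Worked case for #5, with f = 10% and d = 2: b = 0.20 day. At SD 4, b/SE = 1.00 and 1 − Φ(0.96) = 0.169. At SD 10, b/SE = 0.40 and 1 − Φ(1.56) = 0.059.

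| Endpoint | Assumption | Omitted | One-sided error |
|---|---|---|---|
| #5 | 2% × 1 night | 0.02 day | 0.027 to 0.031 |
| #5 | 5% × 2 nights | 0.10 day | 0.039 to 0.072 |
| #5 | 10% × 2 nights | 0.20 day | 0.059 to 0.169 |
| #5 | 20% × 4 nights | 0.80 day | 0.36 to 0.98 |
| #13 to #16 | 2% × 2% | 0.04 point | 0.026 to 0.027 |
| #13 to #16 | 10% × 5% | 0.5 point | 0.047 to 0.068 |
| #13 to #16 | 20% × 10% | 2.0 points | 0.21 to 0.53 |

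For days alive out of hospital, an assumed SD of 60 to 200 days gives an SE of 3 to 10 days. Omitting 0.20 day then gives an error of 0.026 to 0.029, and omitting 0.80 day gives 0.030 to 0.045.

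**The case against.** **The affected group may be small or empty.** A Table 3 footnote says PCI must not occur within 30 days before the index procedure. Combined with the 30-day limit from randomization to procedure, it leaves essentially no room for PCI after randomization and before TAVI. C.4.7.1 allows such a PCI. The objection stands as to size: until the two texts are reconciled, the number of staged subjects cannot be judged. It does not remove the point, because C.4.7.1 expressly recommends staging. Concomitant PCI, which is fully counted, is also the encouraged route, and a Syntax score above 22 and unprotected left main disease are excluded.

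**A reader might infer that PCI complications are lost.** The documents do not support this. Adverse events are collected from enrollment; what is missing is a rule assigning events before Day 0 to an endpoint. A PCI in the same admission as TAVI may already be counted in #5, since the start of the stay is not defined. C.6.5.2 leaves further detail to the SAP; no separate SAP text was available to me, so it should be checked for such a rule.

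**A reader might infer that the cost comparison is biased.** This is not shown. C.6.13.2 says "Data on resource utilization will be collected for the index hospitalization and through long-term follow-up for all enrolled subjects", which leaves the PCI admission unclear, but it places the cost-effectiveness methods in separate documents.

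**A reader might extend the point to #9 and #10.** The arithmetic shows a negligible effect, and the item's own wording points both ways.

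**Equality of the arms is a stress test.** The protocol lists a shorter stay as a potential benefit of TAVI (D.2). If the true difference is large, the omission shifts the estimate without changing the decision. That is fair, but the estimate behind the claim would still favour TAVI.

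**Conclusion.** The point holds for mITT subjects who have PCI staged after randomization, in a separate admission, and then go on to TAVI. For them, the stated Day 0 rule drops PCI nights from #5 and PCI-to-TAVI events from #13 to #16, with no counterpart for CABG in the SAVR arm.

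The direction is clear; the size is not. At 10% staged, about 0.2 day (2 nights each) or about 0.5 percentage point (5% complications) would be omitted. At 2% staged the effect is close to nil. These figures rest entirely on assumed inputs. A general statement that the secondary claims and the economic objective are biased toward TAVI goes beyond the documents. The change is still worth making, because the omission is one-sided, affects labeling claims and costs little to remove.

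**What to change.** - **Counting rule.** Keep visits anchored to TAVI or SAVR. In C.4.9 and C.6.1, state that for #5 and #13 to #16 counting starts in both arms at the first procedure of the assigned strategy (staged PCI, TAVI, or SAVR with or without CABG) and runs through the existing TAVI- or SAVR-based time point. Add the nights of a separate staged-PCI admission to length of stay.
- **Days alive out of hospital.** Use the same start for numerator and denominator, and resolve the conflict in C.6.8.1 item 10 between the post-procedure clock and the inclusion of all hospitalizations.
- **Sensitivity analysis.** Count events and hospital nights from randomization in both arms, so that SAVR subjects' events before surgery are treated alike. Report the revascularization stratum separately.
- **Reconciliation.** C.4.7.1 and the Table 3 footnote on PCI timing before the index procedure must be reconciled. No view is taken here on which should govern.

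The cost is protocol and SAP wording, programming, and confirming that PCI admission and discharge dates are captured; adverse events are already collected from enrollment. The downsides are slightly less favourable TAVI figures and, for staged subjects, a counting window longer by the PCI-to-TAVI gap.
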